**CONFIDENTIAL**

## 4.6. Interim Analyses

An informal interim analysis of the primary endpoint will be conducted following completion of Part 1 of the study, with possible progression to Part 2 based on the following criteria:

CCI

The interim analysis will be conducted after Part 1 is complete. Safety listings for AEs, Labs, ECG, and concomitant medications will be created by Data Management team. The two primary PK outputs, for PK variables  $AUC_{(0-\infty)}$  and  $C_{max}$ , will be created based on plasma concentration data and nominal time. Actual time may also be used as data permit. See [section 4.2.2](#) for details of analysis method.

Based on the decision after interim analysis review, the first criterion is met. Mild HI participants will not be enrolled in Part 2 and only severe HI participants will be enrolled in Part 2.

## 5. SAMPLE SIZE DETERMINATION

Eight participants will be enrolled in each HI group (i.e., Groups 1, 3, and 4). Eight healthy participants will be enrolled in Group 2 and 8 to 16 healthy participants in Group 5 will be enrolled with normal hepatic function, matched to the age ( $\pm 10$  years), weight ( $\pm 20\%$ ), race and gender (1:1) of a participant in Group 1, 3, and/or 4.

CCI

**CONFIDENTIAL**

## **6. SUPPORTING DOCUMENTATION**

### **6.1. Appendix 1 Study Population Analyses**

Unless otherwise specified, the summary will also be grouped by cohort (mild HI, moderate HI, severe HI and matched healthy controls to moderate HI, matched healthy controls to mild and severe HI and pooled healthy controls) for Screened, Enrolled and Safety Analysis Sets.

In this multi-centre global study, enrolment will be listed by site.

#### **6.1.1. Participant Disposition**

A summary of the number and percentage of participants who completed the study as well as those who prematurely withdrew from the study will be provided. Reasons for study withdrawal will be listed and summarized.

A summary of study intervention status will be provided. This display will show the number and percentage of participants who have completed the scheduled study intervention, or have discontinued study intervention prematurely, as well as primary reasons for discontinuation of study intervention.

A summary of analysis populations and listing of subjects excluded from any analysis set based on the Screened Analysis Set described in [Section 3](#) will be provided. In this summary table, the number and percentage participants in each of the analysis set (Screened/ Enrolled/ Assigned/ Safety/ PK) will be produced.

#### **6.1.2. Demographic and Baseline Characteristics**

The demographic characteristics including age, gender, ethnicity, race, height/weight/body mass index (BMI) and HI status at baseline will be summarized with descriptive statistics based on the Safety Analysis Set.

Demographic characteristics will also be listed. It will include baseline HI status (Child-Pugh classification) and clinical and biochemical parameters (encephalopathy grade, ascites, serum bilirubin, serum albumin, prothrombin time, prothrombin time) at baseline.

Past medical conditions and current medical conditions including CV events as of screening will be listed and summarized by cohort respectively.

#### **6.1.3. Protocol Deviations**

Important protocol deviations will be listed and summarized. The summary table will be grouped by cohort and total based on Enrolled Analysis Set.

**CONFIDENTIAL**

Protocol deviations will be tracked by the study team following the Protocol Deviation Rules throughout the conduct of the study. These protocol deviations will be reviewed to identify those considered as important as follows:

- Data will be reviewed prior to freezing the database to ensure all important deviations (where possible without knowing the study intervention details) are captured and categorized in the protocol deviations dataset.
- This dataset will be the basis for the summaries of important protocol deviations.

Participants with I/E criteria deviations will also be listed.

#### **6.1.4. Prior and Concomitant Medications**

Concomitant medications and Anatomical Therapeutic Chemical (ATC) Classification (level 4)/preferred term (PT) will be listed by participant in Enrolled Analysis Set and coded using the most current version September 2023 or higher of WHO Drug dictionary.

Concomitant medications include any medication that was taken at some point during the on-intervention period as defined in Section 6.8 of the protocol.

### **6.2. Appendix 2 Data Derivations Rule**

#### **6.2.1. Criteria for Potential Clinical Importance**

Reference ranges for all laboratory parameters collected throughout the study are provided by the laboratory. A laboratory value that is outside the reference range is considered either high abnormal (value above the upper limit of the reference range) or low abnormal (value below the lower limit of the reference range). Note: a high abnormal or low abnormal laboratory value is not necessarily of clinical concern.

In addition, the following criteria will be used to flag potential clinical importance (PCI):

Parameters	Unit	PCI Range
QTc	msec	Participants with bundle branch block: <450 at baseline and >500 at post-baseline; 450-480 at baseline and $\geq 530$ at post-baseline
QTcF interval	msec	>500; change from baseline >60
ALT-absolute	U/L	$\geq 3 \times \text{ULN}$
ALT and Total Bilirubin (Direct Bilirubin)	U/L; umol/L; umol/L	ALT $\geq 3 \times \text{ULN}$ and total bilirubin $> 2 \times \text{ULN}$ ( $> 35\%$ direct bilirubin)

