7.1.1. Liver chemistry stopping criteria

Discontinuation of study intervention for abnormal liver tests is required by the investigator when a participant meets one of the conditions outlined in the algorithm or in the presence of abnormal liver chemistries not meeting protocol-specified stopping rules if the investigator believes that it is in best interest of the participant.

Study intervention will be discontinued for a participant if liver chemistry stopping criteria are met.

Due to this being a single dose study, participants will not be discontinued from treatment; however, the monitoring/follow-up criteria will apply.

Phase 1 Liver Chemistry Stopping Criteria – Liver Stopping Event Algorithm

Abbreviations: ALT = alanine transaminase; INR = international normalized ratio; SAE = serious adverse event; ULN = upper limit of normal.

Refer to Section 10.6 (Appendix 6) for required Liver Safety Actions and Follow-up Assessments.

For participants with hepatic impairment, liver function tests may be above ULN at baseline. Recruitment and dosing will be stopped, and a safety review will occur following any of the below events:

- Elevation of total bilirubin or hepatic transaminases (within an 8-day window post-dose) beyond the following thresholds:
 - ALT or AST $\geq 3 \times \text{ULN}$ starting from a baseline in the reference range;
 - Increase in ALT or AST $> 150 \text{ U/L}$ for males or $> 100 \text{ U/L}$ for females starting from a baseline outside the reference range
 - A ≥ 2.5 -fold elevation of ALP and/or gamma glutamyl transferase (GGT) relative to the baseline result;
 - Total bilirubin $> 3 \times \text{ULN}$, with $> 50\%$ being direct; starting from a baseline in the reference range;
 - Increase in total bilirubin by 2.5 mg/dL starting from a baseline outside of the reference range;

Note: These findings must be verified by repeated testing following initial observation, OR be part of an upgoing trend.

- Any other event deemed by the Investigator or Sponsor to reflect potentially unacceptable risk to subsequent participant associated with further dosing.

- Severe TEAE or SAE related to IP.

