### **4.3. Secondary Endpoints Analyses**

#### **4.3.1. Secondary endpoints**

##### **4.3.1.1. Definition of endpoints**

*Safety Endpoints:*

- Incidence of AEs, SAEs, AESIs.
- Incidence of participants with clinically relevant changes in clinical laboratory tests, ECG and vital signs assessments.

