### **4.5.3. Additional Safety Assessments**

#### **4.5.3.1. Laboratory Data**

Laboratory summaries will be presented by cohort. Absolute values and change from baseline in laboratory parameters will be summarized with descriptive statistics by timepoint. All laboratory data related to chemistry, hematology, urinalysis and other laboratory characters will be listed separately for participants. A listing will be produced including laboratory data with character results. Shift tables describing out of reference range shifts will be provided for clinical laboratory (hematology and chemistry) results.

Liver function laboratory tests and pregnancy tests (for female only) will be included with chemistry lab tests.

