**CONFIDENTIAL**

Parameters	Unit	PCI Range
ALT and INR		ALT $\geq 3 \times$ ULN and INR>1.5

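### The SAP's liver flags ignore baseline and require ALT of at least 3×ULN, so they do not match the protocol's own baseline-dependent criteria for hepatically impaired participants

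*SAP*

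**What the plan says.** **Endpoint.** SAP 4.3.1.1 lists as a secondary safety endpoint: "Incidence of participants with clinically relevant changes in clinical laboratory tests, ECG and vital signs assessments". Section 4.3.1.2 sends the analysis to 4.5. The visible text of neither section gives a rule for deciding who has had such a change.

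**Flags.** SAP 6.2.1 states: "In addition, the following criteria will be used to flag potential clinical importance (PCI". The liver rows are:
- ALT of at least 3×ULN;
- that ALT level with total bilirubin above 2×ULN, more than 35% of it direct;
- that ALT level with INR above 1.5.

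The QT rows of the same table do use baseline. The QTcF row includes "change from baseline >60", and the bundle-branch-block row sets its limit by the baseline value.

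**Protocol criteria for HI.** Protocol 7.1.1 says: "For participants with hepatic impairment, liver function tests may be above ULN at baseline". For an abnormal baseline it gives an ALT or AST increase above 150 U/L (men) or 100 U/L (women) and, for bilirubin, "Increase in total bilirubin by 2.5 mg/dL starting from a baseline outside of the reference range". For ALP and GGT it uses a rise of at least 2.5-fold on baseline. These apply within 8 days of dosing and need confirmation by repeat testing or an upward trend.

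**Other laboratory outputs.** SAP 4.5.3.1 says: "Shift tables describing out of reference range shifts will be provided for clinical laboratory (hematology and chemistry) results". It also plans summaries of change from baseline by cohort and timepoint. SAP 4.5.3.1.1 adds a listing of liver monitoring that refers to protocol 7.1.1.

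**Entry.** Protocol 5.1.1.1 admits HI participants with bilirubin up to 6 mg/dL and lists no ALT ceiling. Protocol 5.1.1.2 requires normal AST, ALT and bilirubin in controls.

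**The concern.** The endpoint concerns change, and the safety objective compares HI participants with healthy controls. The two populations differ by design on exactly the tests being flagged, and more so now that SAP 2.0 has dropped the mild cohort, leaving moderate and severe HI. A flag with no baseline condition cannot tell an abnormality brought into the study from one that arose after dosing. A flag that always requires high ALT cannot respond to worsening in bilirubin, AST, ALP or GGT alone.

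At stake is the laboratory part of the safety comparison. These flags are the only numerical liver criteria in the SAP, so they are the natural candidate for the incidence count, and they are poorly suited to the HI cohorts. The protocol saw this difficulty and wrote limits for it; the SAP did not carry them into the flags.

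**Working it through.** The plan states no figure for this endpoint, so there is none to reproduce. The check applies the SAP 6.2.1 flags, the reference-range shift category and the protocol 7.1.1 ALT and bilirubin limits to hypothetical participants.

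**Assumptions.** The documents give no ULNs. The cases use ALT 40 U/L (range examined 30 to 75) and bilirubin 1.2 mg/dL (range 1.0 to 1.3). Hence 3×ULN for ALT = 120 U/L and 2×ULN for bilirubin = 2.4 mg/dL. The direct share of bilirubin is taken as 50% or more throughout.

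**1. Cases**

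| Case | Baseline to post-dose | SAP liver flags, baseline / post | Shift | 7.1.1 limit |
|---|---|---|---|---|
| A | ALT 130 to 130; bilirubin 3.0 and INR 1.8, stable | all three / all three | High to High | not met |
| B | ALT 60 to 60; bilirubin 3.0 to 5.5; INR 1.8 | none / none | bilirubin High to High | met: 5.5 − 3.0 = 2.5 mg/dL |
| C | Man, ALT 130 to 290; bilirubin 3.0 and INR 1.8, stable | all three / all three | ALT High to High | met: 290 − 130 = 160, above 150 |
| D | Woman, ALT 50 to 160; bilirubin 1.5 and INR 1.4, stable | none / ALT flag | ALT High to High | met: 160 − 50 = 110, above 100 |

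A is flagged with no change. B reaches the protocol limit with no flag. C has worsened, but its flags are identical before and after dosing. D is handled correctly by the flag. The 7.1.1 column shows only that the numerical limit is reached; the repeat-or-trend condition would still have to be satisfied.

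**2. When entry disease alone raises a flag.** The 6 mg/dL bilirubin ceiling is 6/1.3 = 4.6 to 6/1.0 = 6.0×ULN, far beyond 2×ULN. Even so, no flag is raised unless ALT is at least 3×ULN. Carry-over is therefore confined to participants whose baseline ALT is already at that level.

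**3. Bilirubin.** Case B does not depend on the assumed ULN, provided the baseline is above it: with ALT below 3×ULN, no row of the table can be met.

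**4. ALT.** From an abnormal baseline, the smallest post-dose ALT that meets 7.1.1 lies just above ULN + 100 (women) or ULN + 150 (men). It also reaches 3×ULN when:
- women: ULN + 100 ≥ 3×ULN, so ULN ≤ 50 U/L;
- men: ULN + 150 ≥ 3×ULN, so ULN ≤ 75 U/L.

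At ULN 40 the values are 140 and 190 against 120, so both are flagged. At ULN 55 the value for women is 155 against 165, so a rise could go unflagged.

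**5. Size.** With eight per HI cohort, one participant is 1/8 = 12.5 percentage points of any incidence built on these flags.

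**6. Boundary mismatch.** SAP 6.2.1 uses bilirubin above 2×ULN; protocol 10.3.2 and 10.6 use at least 2×ULN. A value of exactly 2×ULN is classified differently.

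**The case against.** The strongest reply is that worsening is not lost. SAP 4.5.3.1 summarises change from baseline for laboratory parameters by cohort. Protocol 8.3.4 has the investigator record clinically significant changes as AEs, and SAP 4.5.2 tabulates AEs by cohort. A listing is tied to protocol 7.1.1, and a confirmed 7.1.1 event would stop recruitment and dosing for a safety review. With eight per cohort and no hypothesis test, these outputs would show a bilirubin rise such as case B. This stands, and a reader who infers that on-study worsening would go unseen goes too far. What the outputs lack is a prespecified count of participants: the summaries describe distributions, the listing is not a count, and the AE route rests on judgement. Protocol 10.3.1 also excludes abnormalities associated with underlying disease unless they are more severe than expected, and that filter falls mainly on HI participants.

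Three other strong inferences are not supported:
- **That the flags are the endpoint.** The SAP never says so and specifies no incidence table of them. The 12.5-point figure is therefore conditional on their being tabulated.
- **That shift tables record entry disease as change.** They compare baseline with later category, so stable disease appears as High to High. Their weakness is that they cannot show worsening within High.
- **That a typical severe participant would be falsely flagged.** This needs baseline ALT of at least 3×ULN, and the documents give no frequency for that.

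It is also fair that 7.1.1 is an operational hold rule, which a SAP need not reuse. But the SAP offers no other rule suited to abnormal baselines. INR is uncertain: protocol Table 9 lists it under coagulation, Appendix 6 groups it with liver chemistries, and SAP 4.5.3.1 limits shift tables to hematology and chemistry.

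**Conclusion.** The concern holds in a limited form and should be acted on. The liver flags in SAP 6.2.1 are absolute, require high ALT and have no baseline condition, so they do not correspond to the HI criteria in protocol 7.1.1. They flag unchanged disease when baseline ALT is already at least 3×ULN, and give no flag to isolated bilirubin, AST or ALP/GGT worsening. ALT rises that meet 7.1.1 are still flagged at ULNs up to 50 U/L (women) or 75 U/L (men), although they are not separated from entry disease when the baseline was already flagged.

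The more basic gap is that no rule defines a clinically relevant laboratory change. The size is 12.5 percentage points per affected participant if the flags are tabulated; the number affected is unknown. The numerical cases rest on assumed ULNs, but the absence of any flag in case B does not. Part of the chemistry list in protocol Table 9 is redacted and the 7.1.1 algorithm figure is not available, so the conclusion rests on the visible text.

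**What to change.** - **SAP 6.2.1, timing:** count a laboratory flag only when it is met after baseline and was not already met at baseline. The absolute flags can stay in the listings.
- **SAP 6.2.1, abnormal baselines:** for participants whose baseline is outside the reference range, add analysis flags that use the limits already in protocol 7.1.1 for ALT/AST, ALP/GGT and bilirubin, with its repeat-or-trend condition. Let these flags use unscheduled repeats, because SAP 6.2.4 gives scheduled results priority in visit summaries.
- **SAP 4.3.1.2 or 4.5.3.1:** state that these flags feed the incidence of clinically relevant laboratory changes, and tabulate that incidence by cohort.
- **SAP 4.5.3.1:** state whether INR belongs to the shift or the change-from-baseline outputs, and include it in at least one.
- **Bilirubin boundary:** reconcile SAP 6.2.1 with protocol 10.3.2 and 10.6.

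The cost is SAP wording and a few lines of programming, assuming that the tests named in 7.1.1 are in the database. No new clinical threshold is proposed, and the protocol's hold rule and trial conduct are unchanged.

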**CONFIDENTIAL**

Parameters	Unit	PCI Range
ALT and INR		ALT $\geq 3 \times$ ULN and INR>1.5

### 6.2.2. Study Period

Assessments and events will be classified according to the time of occurrence relative to the study intervention period.

**Pre-Intervention** is defined as time prior to the first dose of study intervention.

**On-Intervention** is defined as time from first dose to last date plus five days. If time of assessment or study intervention is not collected, the following assessment on the first dose date will be assumed to be taken prior to the first dose and therefore considered pre-intervention: ECG, Lab, and vital signs, and first dose date is considered on-intervention for AE and concomitant medication.

**Follow-up** is defined 14 + / - 2 days after (inclusive) study drug administration or end of study.

### 6.2.3. Study Day and Reference Dates

The safety reference date is the study intervention start date and will be used to calculate study day for safety measures.

The study day is calculated as below:

- Assessment Date = Missing  
→ Study Day = Missing
- Assessment Date < First Study Administration Date  
→ Study Day = Assessment Date – First Study Administration Date
- Assessment Data  $\geq$  First Study Administration Date  
→ Study Day = Assessment Date – First Study Administration Date + 1

### 6.2.4. Assessment Window

- Actual times will be used in the derivation of PK parameters and in the individual concentration-time plots. Planned times will be used in the descriptive summaries and in mean and median plots. Samples that are collected outside the collection window will be flagged in data listings.
- PK concentration listings shall have both the planned and actual times.
- Planned time will be used for all other analysis.
- For data summaries by visit, the nominal visit description will be used. If there are multiple assessments within the same window, a scheduled visit will be prioritized over un-scheduled visits.

CONFIDENTIAL

### 6.2.5. Handling of Partial Dates

Element	Reporting Detail										
General	
 
Partial dates will be displayed as captured in participant listing displays.
 
However, where necessary, display macros may impute dates as temporary variables for sorting data in listings only. In addition, partial dates may be imputed for 'slotting' data to study phases or for specific analysis purposes as outlined below.
 
Imputed partial dates will not be used to derive study day, time to onset or duration (e.g., time to onset or duration of adverse events), or elapsed time variables (e.g., time since diagnosis). In addition, imputed dates are not used for deriving the last contact date in overall survival analysis dataset.
 
										
Adverse Events	
 
Partial dates for AE recorded in the CRF will be imputed using the following conventions:
 
 
 
 Missing start day	 
If study intervention start date is missing (i.e. participant did not start study intervention), then set start date = 1st of month.
 
Else if study intervention start date is not missing:
 
 
If month and year of start date = month and year of study intervention start date, then 
 
If stop date contains a full date and stop date is earlier than study intervention start date, then set start date = 1st of month.
 
Else set start date = study intervention start date.
 
 
 
 
Else set start date = 1st of month.
 	
 
 Missing start day and month	 
If study intervention start date is missing (i.e. participant did not start study intervention), then set start date = January 1.
 
Else if study intervention start date is not missing:
 
 
If year of start date = year of study intervention start date, then 
 
If stop date contains a full date and stop date is earlier than study intervention start date, then set start date = January 1.
 
Else set start date = study intervention start date.
 
 
 
 
Else set start date = January 1.
 	
 
 Missing end day	A '28/29/30/31' will be used for the day (dependent on the month and year).	
 
 Missing end day and month	No Imputation	
 
 Completely missing start/end date	No imputation	
 
	Missing start day	
If study intervention start date is missing (i.e. participant did not start study intervention), then set start date = 1st of month.
 
Else if study intervention start date is not missing:
 
 
If month and year of start date = month and year of study intervention start date, then 
 
If stop date contains a full date and stop date is earlier than study intervention start date, then set start date = 1st of month.
 
Else set start date = study intervention start date.
 
 
 
 
Else set start date = 1st of month.
	Missing start day and month	
If study intervention start date is missing (i.e. participant did not start study intervention), then set start date = January 1.
 
Else if study intervention start date is not missing:
 
 
If year of start date = year of study intervention start date, then 
 
If stop date contains a full date and stop date is earlier than study intervention start date, then set start date = January 1.
 
Else set start date = study intervention start date.
 
 
 
 
Else set start date = January 1.
	Missing end day	A '28/29/30/31' will be used for the day (dependent on the month and year).	Missing end day and month	No Imputation	Completely missing start/end date	No imputation
Missing start day	
If study intervention start date is missing (i.e. participant did not start study intervention), then set start date = 1st of month.
 
Else if study intervention start date is not missing:
 
 
If month and year of start date = month and year of study intervention start date, then 
 
If stop date contains a full date and stop date is earlier than study intervention start date, then set start date = 1st of month.
 
Else set start date = study intervention start date.
 
 
 
 
Else set start date = 1st of month.
										
Missing start day and month	
If study intervention start date is missing (i.e. participant did not start study intervention), then set start date = January 1.
 
Else if study intervention start date is not missing:
 
 
If year of start date = year of study intervention start date, then 
 
If stop date contains a full date and stop date is earlier than study intervention start date, then set start date = January 1.
 
Else set start date = study intervention start date.
 
 
 
 
Else set start date = January 1.
										
Missing end day	A '28/29/30/31' will be used for the day (dependent on the month and year).										
Missing end day and month	No Imputation										
Completely missing start/end date	No imputation										

